| Complete response (CR) | Absence of serum monoclonal IgM protein by immunofixation Normal serum IgM level Complete resolution of extramedullary disease, i.e., lymphadenopathy and splenomegaly if present at baseline Morphologically normal bone marrow aspirate and trephine biopsy |
| Very good partial response (VGPR) | Monoclonal IgM protein is detectable ≥90% reduction in serum IgM level from baseline ^a Complete resolution of extramedullary disease i.e., lymphadenopathy/splenomegaly if present at baseline No new signs or symptoms of active disease |
| Partial response (PR) | Monoclonal IgM protein is detectable ≥50% but < 90% reduction in serum monoclonal IgM level from baseline ^a Reduction in extramedullary disease i.e., lymphadenopathy/splenomegaly if present at baseline No new signs or symptoms of active disease |
| Minor response (MR) | Monoclonal IgM protein is detectable ≥25% but <50% reduction in serum monoclonal IgM level from baseline ^a No new signs or symptoms of active disease |
| Stable disease (SD) | Monoclonal IgM protein is detectable <25% reduction and <25% increase in serum monoclonal IgM level from baseline ^a No progression in extramedullary disease i.e., lymphadenopathy/splenomegaly No new signs or symptoms of active disease |
| Progressive disease (PD) | ≥25% increase in serum IgM level ^a from lowest nadir (requires confirmation on ≥2 consecutive measurements at least 4 weeks apart). AND Progression of clinical features attributable to the disease per Owen et al. 2013 and Cheson et al. 2014. |

Owen et al. 2013, Cheson et al. 2014

Abbreviations: CR = complete response; Ig = immunoglobulin; MR = minor response; PD = progressive disease; PR = partial response; SD = stable disease; VGPR = very good partial response; WM = Waldenström macroglobulinemia.

Acerta Pharma Confidential Page 93

a. Sequential changes in IgM levels may be determined either by M protein quantitation or total serum IgM quantitation by nephelometry.

Protocol: ACE-LY-001

Table 4-7. Response Assessment Criteria for B-ALL

| Response | Definition |
|-----------------------------------------------|------------------------------------------------------------------------------------------------------------------------------------------------------|
| Complete response (CR) | No circulating blasts or extramedullary disease Trilineage hematopoiesis and <5% blasts ANC >1000/µL Platelets >100,000/µL No recurrence for 4 weeks |

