| Partial response (PR) | ≥50% reduction of serum M-protein and reduction in 24-h urinary M-protein by ≥90% or to <200 mg per 24 h If the serum and urine M-protein are unmeasurable at baseline, a ≥50% decrease in the difference between involved and uninvolved FLC levels is required in place of the M-protein criteria. If serum and urine M-protein are unmeasurable at baseline, and serum free light assay is also unmeasurable, ≥50% reduction in plasma cells is required in place of M-protein, provided baseline bone marrow plasma cell percentage was ≥30%. In addition to the above listed criteria, if present at baseline, a ≥50% reduction in the size of soft tissue plasmacytomas is also required. |
| Minor response (MR) | MR includes subjects in whom some, but not all, criteria for PR are fulfilled providing the remaining criteria satisfy the requirements for MR. Requires all of the following: ○ ≥25% to ≤9% reduction in the level of serum monoclonal protein for ≥2 determinations 6 weeks apart ○ If present, a 50% to 89% reduction in 24-h light chain excretion, which still exceeds 200 mg/24 h, for ≥2 determinations 6 weeks apart ○ 25-49% reduction in the size of plasmacytomas (by clinical or radiographic examination) for ≥6 weeks ○ No increase in size or number of lytic bone lesions (development of compression fracture does not exclude response) |

Protocol: ACE-LY-001

Table 4-8. Response Criteria for MM (incorporating EBMT and IMWG)

| Response Subcategory | Response Criteriaª |
|------------------------------------------------------------------------------------------------------------------------------------------------------------------|--------------------------------------------------------------------------------------------------------------------------------------------------------------------------|
| Stable disease (SD) (not recommended for use as an indicator of response; stability of disease is best described by providing the time to progression estimates) | Not meeting criteria for CR, VGPR, MR, PR, or progressive disease. |
| Progression Subcategory | Progression Criteria ^d |
| Progressive disease ^a — To be used for | Laboratory or biochemical relapse or progressive disease: requires the occurrence of ≥1 of any of the following: |
| calculation of duration of response and progression-free survival | Increase of ≥25% from lowest response value in serum M-component and/or (the absolute increase must be ≥0.5 g/dL)e |

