| end points for all subjects including those in CR (includes primary | Urine M-component and/or (the absolute increase must be ≥200mg/24 h) |
| progressive disease and disease progression on or off therapy) ^g | Only in subjects without measurable serum and urine M-protein levels: the difference between involved and uninvolved FLC levels. The absolute increase must be >10 mg/dL |
| | Bone marrow plasma cell percentage: the absolute % must be ≥10% ^f |
| | Definite development of new bone lesions or soft tissue plasmacytomas or definite increase in the size of existing bone lesions or soft tissue plasmacytomas. |

EBMT (Bladé et al. 1998) and IMWG (Durie et al. 2006)

Abbreviations: CR = complete response; EBMT = European Group for Blood and Marrow Transplant; FLC = (serum) free light chains; IMWG = International Myeloma Working Group; MM = multiple myeloma; MR = minor response; nCR = near complete response; PR = partial response; sCR = stringent complete response; SD = stable disease; VGPR = very good partial response.

Note clarification to IMWG criteria for coding CR and VGPR in subjects in whom the only measurable disease is by serum FLC levels: CR in such subjects a normal FLC ratio of 0.26-1.65 in addition to CR criteria listed above. VGPR in such subjects is defined as a >90% decrease in the difference between involved and uninvolved free light chain FLC levels.

- a. All response categories require 2 consecutive assessments made at ≥4 weeks after the start of study therapy and any time before the institution of any new therapy after study therapy; CR and PR and SD categories also require no known evidence of progressive or new bone lesions if radiographic studies were performed. Radiographic studies are not required to satisfy these response requirements.
- b. Confirmation with repeat bone marrow biopsy not needed.
- c. Presence/absence of clonal cells is based upon the kappa/lambda ratio. An abnormal kappa/lambda ratio by immunohistochemistry and/or immunofluorescence requires a

Protocol: ACE-LY-001

minimum of 100 plasma cells for analysis. An abnormal ratio reflecting presence of an abnormal clone is kappa/lambda of >4:1 or <1:2.

- d. All relapse categories require 2 consecutive assessments made at any time before classification as relapse or disease progression and/or the institution of any new therapy.
- e. For progressive disease, serum M-component increases of ≥1 gm/dL are sufficient to define relapse if starting M-component is ≥5 g/dL.

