- f. Relapse from CR has the 5% cutoff versus 10% for other categories of relapse.
- g. For purposes of calculating time to progression and progression-free survival, CR subjects should also be evaluated using criteria listed above for progressive disease.

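### Table 4-8 prints a serum range for myeloma minor response that no value can satisfy, and leaves open which marrow cut-off dates progression after CR

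*Protocol*

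**What the plan says.** **Minor response.** The MR row of Table 4-8 lists limbs that must all be met. The serum limb is "≥25% to ≤9% reduction in the level of serum monoclonal protein for ≥2 determinations 6 weeks apart". The plasmacytoma limb in the same cell is "25-49% reduction in the size of plasmacytomas (by clinical or radiographic examination) for ≥6 weeks". The PR row directly above asks for "≥50% reduction of serum M-protein and reduction in 24-h urinary M-protein by ≥90% or to <200 mg per 24 h". Stable disease is the residual class: whatever is not CR, VGPR, PR, MR or progression. The MR row also opens with a mixed rule. A subject may fulfil some of the PR criteria, provided that the remaining ones satisfy the MR requirements.

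For comparison, the MR range for Waldenström macroglobulinemia in Table 4-6 is "≥25% but <50% reduction in serum monoclonal IgM level from baseline".

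**Marrow progression.** The progressive-disease row of Table 4-8 says that its criteria serve duration of response and PFS for every subject, including those in CR. Its marrow limb reads "Bone marrow plasma cell percentage: the absolute % must be ≥10" (per cent) and carries footnote f: "Relapse from CR has the 5% cutoff versus 10% for other categories of relapse". Footnote g says that, for time to progression and PFS, "CR subjects should also be evaluated using criteria listed above for progressive disease".

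**Use of the table.** Section 5.4.4 defines ORR through Tables 4-4 to 4-8 and does not say whether MR counts as a response.

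**The concern.** These are operative criteria. The investigator classifies myeloma response from Table 4-8, and section 5.4.4 builds the efficacy endpoints on that classification.

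An empty range in a limb that must be met blocks one route into MR and sends those subjects to stable disease. Someone who notices the error may silently substitute a bound, and different sites may substitute different ones.

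The marrow point concerns dates. If one reader applies 5% and another 10% to the same CR subject, one records an event and the other does not. That bears on PFS and duration of response. Because section 3.12 ties confirmed progression to withdrawal from treatment, it also bears on conduct.

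**Working it through.** No sample-size or power figure underlies this point, so the check is logical, with one piece of arithmetic for size.

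**1. The serum limb as printed.** Let x be the percentage reduction in serum M-protein. The limb requires x ≥ 25 and x ≤ 9. Since 25 > 9, the set is empty. A scan in steps of 0.1 point also returns no qualifying value.

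**2. What the neighbouring limits imply.**

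| Place | Range or threshold |
|---|---|
| MR plasmacytoma limb, same cell | 25% to 49% |
| PR serum criterion, row above | 50% or more |
| MR in Waldenström macroglobulinemia, Table 4-6 | 25% to below 50% |

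All three point to an upper bound just below 50%. A bound of ≤49% would give 25.0 to 49.0 and leave values between 49% and 50% unclassified. A bound of <50% meets the PR threshold with no gap.

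**3. Who is affected as printed.**
- Serum fall of 25% to below 50%: PR is not met on serum and the MR serum limb cannot be met, so the subject defaults to stable disease if there is no progression. This holds even if the urine result is at PR level, because the remaining criterion, serum, must still satisfy MR.
- Serum fall of 50% or more, with a light-chain fall of only 50% to 89% still above 200 mg per 24 h: the PR serum criterion is met and the MR light-chain limb is met. If any plasmacytomas also meet their limb and the lytic-lesion condition holds, MR is reachable as printed.

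**4. Size.** Section 3.0 allows up to 12 subjects per histology. One reclassified subject in a full group is 1/12 = 8.3 points. Section 3.10.3 splits the myeloma group into a first 6 without and a last 6 with dexamethasone, so within either half one subject is 1/6 = 16.7 points. These are shifts in ORR only if MR is counted as a response. If it is not, ORR does not move.

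**5. Marrow cut-offs for a CR subject with no other progression criterion met.**

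| Marrow plasma cells | 5% cut-off | 10% cut-off |
|---|---|---|
| 4% | no event | no event |
| 5% | event | no event |
| 7% | event | no event |
| 9.9% | event | no event |
| 10% | event | event |
| 12% | event | event |

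The two readings differ only from 5% to below 10%. Footnote d also requires two consecutive assessments. Section 4.1.22 calls for on-study marrow in myeloma only to confirm CR or when clinically indicated, so few such values will exist.

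**The case against.** **The misprint may not be in the protocol.** The text available here was extracted from a PDF, and other symbols in the response tables came through garbled. A dropped 4 from 49 cannot be excluded. This stands: the source page must be checked first, and if it reads 49 the serum point falls away.

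**The intended bound is obvious.** An investigator would probably infer it from the same cell. That lowers the likelihood of harm, but it does not make the criterion correct.

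**A reader might infer that the whole MR category is lost.** The document does not support that. The opening sentence of the MR row keeps MR open to a subject who meets the PR serum criterion and falls short on another limb. Only the route through the serum limb is closed.

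**A reader might infer that ORR is wrong.** The protocol's efficacy endpoints are ORR, duration of response, PFS and time-to-next treatment; there is no MR rate among them. Which categories count towards ORR is commonly settled in the SAP, which is not shown, so the silence of section 5.4.4 is treated here as a condition and not as a fault.

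**A reader might call the two marrow cut-offs a flat contradiction, or a threshold that cannot be applied.** Footnote f is attached to the 10% limb itself. It can be read as an exception within the criteria to which footnote g refers, and it fits a CR defined by fewer than 5% plasma cells. Footnote g gives no number of its own. What survives is an ambiguity: the row heading and footnote g send CR subjects to the progression criteria without saying whether the exception travels with them.

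**Reach is small.** This is one histology with at most 12 subjects, closed to enrollment since Amendment 4, and activity is a secondary objective. All of that stands.

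**Conclusion.** The serum limb for myeloma MR is wrong as written. It admits no value, and a fall of 25% to below 50% without progression becomes stable disease by default. This assumes that the printed page matches the extracted text.

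The consequence for ORR is conditional: 8.3 points per affected subject if MR counts as a response and the group had its full 12, and zero if MR does not count. The protocol gives no actual myeloma enrollment; in a smaller group each subject would weigh more.

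The MR error moves no progression date. Nothing in the document shows that any subject has in fact been misclassified, so it would go too far to say that response classes or progression dates are misassigned.

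The marrow point is a separate and narrower ambiguity. It can change the event status of a CR subject with 5% to below 10% plasma cells and no other progression criterion, and of nobody else. The document does not settle which cut-off is meant, and this review does not choose one.

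**What to change.** 1. Check the MR serum limb on the source page of Table 4-8.
2. If it is printed as extracted, correct the upper bound so that the range runs up to the PR threshold, for example ≥25% but <50%. That agrees with the plasmacytoma limb and with Table 4-6, and it leaves no gap below PR. The sponsor should confirm the intended bound.
3. Recheck any myeloma response calls already entered, looking for stable-disease entries with a serum fall of 25% to below 50%.
4. Reconcile footnotes f and g with the heading of the progression row, in one sentence naming the marrow cut-off that dates PFS and duration of response for CR subjects. Because progression also bears on withdrawal under section 3.12, the choice belongs to the sponsor.

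The cost is one corrected bound, one clarifying sentence and a short data check in a group of at most 12. No new data are needed.

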4.3 TT AND SFU VISITS

A TT visit is required for safety assessments for any subjects who permanently discontinue study treatment early for any reason including disease progression. The TT visit should be scheduled within 7 days of the last dose of study dose, if possible, and is not required for subjects who discontinue from the study within 10 days of a scheduled study visit.

Each subject should be followed until the SFU visit at 30 (+7) days after his or her last dose of study drug to monitor for resolution or progression of AEs (see Section 6.3.6) and to document the occurrence of any new events, regardless of whether the subject receives a new anticancer therapy or demonstrates disease progression within this timeframe. Subjects should bring any remaining capsules to the clinic at the SFU visit. Subjects who withdraw consent for study treatment should still be encouraged to complete the SFU assessments, but these assessments cannot be mandated if subject consent for further study participation is withdrawn. If the TT visit and the SFU visit coincide, then these can be combined into 1 visit. The schedule of assessments (Appendix 5) describes the procedures required for the TT and SFU visits.

4.4 DISCONTINUATION FOLLOW-UP FOR PROGRESSION AND TIME-TO NEXT TREATMENT

Each subject should be followed until disease progression or the start of alternative anticancer therapy. If neither of these has occurred at the time of the 30-day SFU visit, DFU visits should occur approximately every 3 months until disease progression or next anticancer treatment. During this period, subjects will be followed via CBC, and CT scans per investigator discretion. Refer to Appendix 5 for the full list of assessments required during this period.

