3.1.3 Efficacy Parameters

Standardized response and progression criteria have been established for B-cell malignancies, including WM (Bladé et al. 1998; Durie et al. 2006; Hallek et al. 2008; Owen et al. 2013; and Cheson et al. 2014); assessments of acalabrutinib and ACP-319 efficacy in this study will be based on these criteria. Efficacy endpoints will include:

Overall response rate (ORR)

Duration of response

Progression-free survival

Time-to-next treatment

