Any subject who becomes significantly noncompliant with study drug administration, study procedures, or study requirements should be withdrawn from study treatment in circumstances that increase risk or substantially compromise the interpretation of study results.

Subjects who discontinue study therapy will continue on study for safety (Section 4.3), disease progression, and time-to-next therapy (Section 4.4) for their lymphoid cancer unless they withdraw consent for further follow-up. Thus, all subjects receiving ≥1 dose of study drug will be followed during the immediate post-therapy period unless the subject withdraws consent for such follow-up to be conducted. The date the subject is

Protocol: ACE-LY-001

withdrawn from study treatment or from the study (including post-therapy follow-up) and the reason for discontinuation will be recorded and also should be described on the appropriate CRF.

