3.13 REASONS FOR STUDY EXIT

Reasons for study exit include:

Subject's withdrawal of consent from study

Decision by sponsor to terminate the study

Disease progression

Start of alternative anticancer therapy

Subject lost to follow-up

Death

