Time-to-next treatment defined as the time from start of acalabrutinib and ACP-319 therapy on this protocol to the start of the next treatment. Kaplan-Meier methods will be used to estimate the event-free curves and corresponding quantiles (including the median). Data from subjects who have not received subsequent therapy will be censored at the earliest of death or the last time that lack of administration of a new therapy was objectively documented.

Protocol: ACE-LY-001

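### Apart from the 30 (+7)-day safety visit, planned follow-up ends at disease progression, so later next-treatment starts are not captured and Kaplan-Meier time-to-next treatment is biased upward

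*Protocol*

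**What the plan says.** TTNT is part of the third secondary objective (Section 2.2) and one of four efficacy endpoints (Section 3.1.3: "Time-to-next treatment"). Section 5.4.4 defines it: "Time-to-next treatment defined as the time from start of acalabrutinib and ACP-319 therapy on this protocol to the start of the next treatment". It is estimated by Kaplan-Meier. Progression is neither an event nor a censoring reason. On censoring: "Data from subjects who have not received subsequent therapy will be censored at the earliest of death or the last time" at which absence of a new therapy was documented.

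The follow-up rules are these:

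- Section 4.4: "Each subject should be followed until disease progression or the start of alternative anticancer therapy". If neither has occurred by the SFU visit, "DFU visits should occur approximately every 3 months until disease progression or next anticancer treatment". The synopsis, Section 3.0 and Appendix 5 footnote d give the same rule.
- Section 3.13 lists "Disease progression" among the reasons for study exit.
- Section 4.3 follows every subject to the SFU visit, 30 (+7) days after last dose, whether or not the subject has progressed or started another therapy. Appendix 5 collects TTNT at the SFU and discontinuation follow-up (DFU) visits.
- Section 3.12: "Subjects who discontinue study therapy will continue on study for safety (Section 4.3), disease progression, and time-to-next therapy (Section 4.4"). The section it cites is the one that stops at progression.

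**The concern.** Section 3.10.2 prohibits other treatment for the lymphoid cancer on study, and Section 3.12 withdraws subjects with confirmed progression from study treatment. The next treatment will therefore usually start after progression. A follow-up rule that ends at progression or new therapy, whichever is first, suits progression-free survival but not TTNT.

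Kaplan-Meier assumes that a censored subject has the same later chance of the event as those still under observation. Here the censored subjects have just progressed and are more likely than others to start a new therapy soon. Censoring them removes the high-risk part of the experience, and the curve stays too high. The trial would then report that the regimen defers further therapy for longer than it did. An analysis plan cannot repair this, because the missing dates are never scheduled for collection.

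**Working it through.** **1. Passages side by side.** The word *or* in Section 4.4 cannot be read as following subjects until both events have occurred, because DFU visits are conditional on neither having occurred by SFU. Scheduled capture of the next treatment is therefore:

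| Subject | Last scheduled contact that collects TTNT |
|---|---|
| Starts new therapy without progression | The start itself (event observed) |
| Progresses on study drug | SFU, 30 (+7) days after last dose |
| Stops drug earlier, progresses during DFU | The DFU contact at which progression is found |

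**2. The plan's own figure.** The protocol gives no expected event count, rate or median for TTNT, so there is nothing to reproduce. Sizes below rest on assumptions and show a range.

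**3. Share of post-progression starts captured.** Assume that last dose is at progression, that time from progression to next therapy is exponential with mean g months, that survival after progression is exponential with mean 8 months and independent of the gap, and that contact ends w months after progression. Among subjects who would start a next therapy before dying, the share who start within w is

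captured = 1 − exp[−(1/g + 1/8) × w]

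With w = 1:
- g = 1: 1 − exp(−1.125) = 67.5%, about 68%
- g = 2: 1 − exp(−0.625) = 46.5%, about 47%
- g = 4: 1 − exp(−0.375) = 31.3%, about 31%

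For g = 2 with a longer window:
- 37 days (w = 37/30.44 = 1.216): 1 − exp(−0.760) = 53%
- 2 months: 1 − exp(−1.25) = 71%
- 3 months: 1 − exp(−1.875) = 85%

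For a progression found during DFU, w = 0 and scheduled capture is 0%.

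**4. Effect on the Kaplan-Meier median.** Simulation of 400,000 subjects per scenario. Further assumptions: exponential progression-free survival with median 6 months, 20% of those events deaths, no starts before progression, administrative end at 36 months. Death is censored in both columns, as Section 5.4.4 prescribes.

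| Mean gap | Median TTNT, contact ends 1 month after progression | Median TTNT, contact continued |
|---|---|---|
| 1 month | about 13 months | 9.2 months |
| 2 months | 21.0 months | 10.8 months |
| 4 months | not reached | about 13.8 months |

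For the 2-month gap, lengthening the window brings the estimate down: 18.5 months (37 days), about 14.1 (2 months), 12.2 (3 months), against 10.8 with continued contact. The direction was the same for progression-free survival medians of 4, 6 and 12 months at all three gaps.

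**5. A second set of assumptions.** No deaths, progression-free survival median 6 months, 10% of subjects starting next therapy before progression, last dose at progression, and gaps given as medians:

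| Median gap | Continued contact | SFU at day 30 | SFU at day 37 |
|---|---|---|---|
| 0.5 month | 6.2 months | 7.7 | 7.2 |
| 1 month | 7.0 months | 11.2 | 10.0 |
| 2 months | 8.4 months | 17.9 | 15.7 |

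The share of all TTNT events captured at day 30 / day 37 is 77% / 83%, 55% / 61% and 36% / 41%. The estimate was above the true curve in every scenario run.

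**The case against.** Five points can be made for the plan.

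- **Contact does not stop at progression for everyone.** This stands. Every subject who progresses on drug has the SFU visit, and TTNT is collected there. Sections 3.0 and 3.12 also allow study drug to continue for a time after progression or while it is being confirmed, which moves last dose and SFU later. This shrinks the bias but does not remove it, and it does nothing for a progression found during DFU.
- **A reader might infer that most next treatments are lost.** The documents do not support that, because they do not give the gap. With a mean gap of 1 month about two thirds are captured. With a mean gap of 2 months, moving from a 1-month to a 37-day window shifts capture from 47% to 53%.
- **Other contacts exist.** Section 4.1.24 asks for monthly CMV testing until 12 months after the last dose of ACP-319, and Section 4.1.13 has a similar rule for anti-HBc-positive subjects on combination therapy. Neither makes an exception for progression. But neither schedules collection of next therapy, and both sit badly with study exit at progression.
- **Censoring at death might be called an error too.** It is a clearly stated definition. A competing-event or composite summary answers a different question and is optional.
- **The stakes are limited.** This stands. The primary objective is safety and the primary efficacy endpoint is response rate. TTNT is descriptive, in a single-arm study with expansion groups of up to 12 per histology, so it will be imprecise in any case.

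**Conclusion.** The concern holds in a limited form. Apart from the SFU visit, planned follow-up ends at progression, in conflict with the stated intent of Section 3.12. Next treatments started later are not scheduled for capture, the censoring is informative, and Kaplan-Meier TTNT is biased upward.

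The direction rests only on next therapy being more likely soon after progression than before it. The size rests on two quantities that the documents do not give: the gap from progression to next therapy, and how long study drug continues past progression. Over the assumed ranges above, it runs from about one month on the median (7.2 or 7.7 against 6.2) to a median that is not reached against about 13.8 months.

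Response rate and progression-free survival are not affected. The change should be made, but it is not a condition for the trial's primary results to stand.

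**What to change.** - **Follow-up.** In the synopsis, Sections 3.0, 3.12, 3.13 and 4.4, and Appendix 5 (footnote d), continue a 3-monthly phone or chart contact after progression, solely for date of next anticancer therapy and date of death. End it at next therapy, death, withdrawal of consent or end of study. For this purpose, remove progression as a reason for study exit. All six places must change together, or a new contradiction replaces the old one.
- **Subjects already exited.** An amendment now cannot reach them prospectively. Retrieve next-therapy dates from charts where consent allows. Where that is not possible, report TTNT as biased upward and not reliably estimable.
- **Optional.** Add a cumulative-incidence summary with death before next therapy as a competing event, beside the current definition.

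The cost is an amendment touching six places, a short contact form, a small amount of site work every 3 months, and the chart retrieval. No extra clinic visits or scans are needed.
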